In formulating our study design, we also considered what happens among those individuals who are on ART, interrupt therapy and eventually achieve control (“post-treatment controllers”) as this is the clinical phenotype we are trying to generate therapeutically. Few studies have carefully characterized the acute viremic stage in post-treatment controllers. In a recent study performed at the NIH, people who started therapy during early infection, stopped therapy and eventually exhibited some degree of control generally but not universally had a brief period of relatively low-level viremia. Still, some had very high-level viremia for a few weeks (see Figures)⁵

Similar data were recently reported by an extended collaboration that included several post-treatment controllers from our group (the CHAMP Cohort)¹³².

Based on this rationale, we propose that in addition to the standard CD4+ T cell count criteria (confirmed decline to below 350 cells/mm³) and clinical criteria (acute retroviral syndrome) that treatment be initiated for any one of the following outcomes: (1) viremia > 50,000 copies RNA/mL for four weeks, (2) viremia > 10,000 copies RNA/mL for 6 weeks, (3) viremia > 2000 copies RNA/ml for 12 weeks or (4) viremia > 400 copies/RNA for 24 weeks. Operationally, this will allow for an acute viremic state that will need to resolve within four to 12 weeks, with high-level viremia only being allowed for a brief period. Post-treatment control (defined as viremia < 400 copies RNA/mL) should be achieved prior to Week 24 post-virus rebound, or ART will be initiated.

In addition to these viral load criteria, we will resume therapy for a confirmed decline in CD4+ T cell count to less than 350 cells/mm³ or clinical symptoms, including the acute retroviral syndrome, which is discussed below.

We are aware that interrupting ART has potential for significant risks. We will use a conservative study design to minimize risk. All individuals will be on a regimen that includes antiretroviral drugs with rapid clearance. This will minimize the chance that drugs will persist long enough to select for drug resistance in the rebounding virus. We will only include individuals with high CD4+ T cell counts to minimize the risk of developing clinically relevant immunodeficiency once the virus rebounds. We will monitor

individuals during the study, and resume therapy for a persistently high viral load, low CD4+ T cell count or the development of symptomatic disease.

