We have been using this EDDI in our cohort for years. We will use this approach to identify our population.

Our group has also calculated the estimated infection date (EID) using clinical history and an analysis of the antibody profiles, as characterized using the Western Blot. These calculations are listed in order of preference as outlined below:

- 1) First Positive Test at Options = Negative EIA and/or Negative Western Blot with detectable viral load. Positive Western Blot confirmed by subsequent repeat testing. EID = 24 days before date of first positive test.
- 2) First Positive Test = Indeterminate Western Blot. Positive Western Blot confirmed by subsequent repeat testing. EID = 24 days before date of first positive test.
- 3) First Positive Test = Positive Western Blot. Copy available showing last Negative HIV test within 180 days. EID = 24 days before the midpoint between last negative test and first positive test.

We will recruit HIV-infected adults who started ART in early infection from our local cohort (Options) and from other centers in the city. As the method used to diagnose early infection has varied over the past two decades and across centers, we will use either the Fiebig, EDDI or EDI system outlined above to define acute/early infection. We will seek to enroll individuals who appeared to start ART during early infection (first six months) using any of these classification systems.

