6.2 Inclusion Criteria

1. Willing and able to provide written informed consent
2. Male, female, or transgender
3. Age ≤ 65 years at the time of enrollment.
4. HIV-1 infection, documented by any of the following:
 - a. licensed rapid HIV test or HIV enzyme or chemiluminescence immunoassay (E/CIA) test kit at any time prior to study entry and confirmed by a licensed Western blot or a second antibody test by a method other than the initial rapid HIV and/or E/CIA
 - b. 4th Generation HIV-1 Ag/Ab test
 - c. HIV-1 antigen or plasma HIV-1 RNA viral load as confirmed by the Principal Investigator
 - d. Research assay result compatible with a diagnosis of HIV infection (e.g. detectable intracellular HIV DNA or viral outgrowth assay) as confirmed by the Principal Investigator
5. On continuous antiretroviral therapy for at least 12 months without any interruptions of greater than 14 consecutive days within the last 1 year, and on a stable regimen that does not include a non-nucleoside reverse transcriptase inhibitor (NNRTI) for at least 4 weeks at the time of first study product administration, without plans to modify ART during the study period
6. ART initiated within 6 months of estimated infection date (early ART, n=15) or after six months of their estimated infection date (late ART, n=5). A participant must meet the definition for Early infection using an estimated infection date by at least one method: EID, EDDI, or Fiebig staging (I-V) at diagnosis.
7. Screening plasma HIV RNA levels below the level of quantification on all available determinations in past 12 months (isolated single values above the level of quantification but < 200 copies/mL will be allowed if they were preceded and followed by unquantifiable viral load determinations)

8. Screening CD4+ T-cell count ≥ 500 cells/mm³
9. Creatinine Clearance (CrCl) > 60 mL/min via Cockcroft-Gault method at screening
10. The following laboratory criteria must be met at screening:
 - Absolute neutrophil count (ANC) ≥ 1000 neutrophils/mm³
 - Hemoglobin ≥ 10.0 g/dL
 - Platelet count $\geq 100,000$ /uL
 - Aspartate aminotransferase (AST) ≤ 2 x upper limit of normal (ULN)
 - Alanine aminotransferase (ALT) ≤ 2 x ULN
 - Total, direct and indirect bilirubin \leq ULN

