8. Evidence of HIV “elite” control prior to ART as defined by having HIV RNA levels below the limit of detection without exposure to ART, using commercially available assays at that time
9. History of current active hepatitis B (HBV) infection defined as positive HBV surface antigen test.

10. Active hepatitis C (HCV) infection. Subjects must be HCV antibody negative or have evidence of cleared HCV infection. If the subject HCV antibody positive, an unquantifiable HCV RNA result (<LLOQ, either target detected or target not detected) within 42 days prior to study entry is required. Those who are currently receiving HCV antiviral therapy or those who have received HCV treatment in the last 6 months prior to study entry will be excluded.
11. Chronic liver disease including known compensated cirrhosis or uncompensated cirrhosis, as defined by the presence of ascites, encephalopathy, esophageal or gastric varices, or persistent unexplained jaundice.
12. Active and poorly controlled atherosclerotic cardiovascular disease (ASCVD), as defined by 2013 ACC/AHA guidelines, including a previous diagnosis of any of the following: (a) acute myocardial infarction, (b) acute coronary syndromes, (c) stable or unstable angina, (d) coronary or other arterial revascularization, (e) stroke, (f) transient ischemic attack (TIA), or (g) peripheral arterial disease presumed to be of atherosclerotic origin.
13. Presence of significant abnormalities on electrocardiogram
14. History of potential immune-mediated medical conditions (see Appendix A). Individuals with isolated Raynaud's phenomenon or localized disease requiring topical therapy alone will not be excluded.
15. Serious illness requiring systemic treatment and/or hospitalization in the 3 months prior to study enrollment
16. Concurrent treatment with immunomodulatory drugs, and/or exposure to any immunomodulatory drug in the 4 weeks prior to study enrollment (e.g. corticosteroid therapy equal to or exceeding a dose of 15 mg/day of prednisone for more than 10 days, IL-2, interferon-alpha, methotrexate, cancer chemotherapy). use of inhaled or nasal steroid is not exclusionary.

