15.4 Primary Efficacy Endpoint: Post-treatment Control

All subjects will undergo a treatment interruption designed to evaluate the primary outcome of “post-treatment control” (PTC), using the definition we recently used as part of the CHAMP Cohort collaboration¹³². In this study, PTCs were defined as individuals who remained off ART for ≥ 24 weeks and maintained viral loads ≤ 400 copies/mL for at least 2/3 of the time points. Viral loads > 400 HIV-1 RNA copies/mL were acceptable if the participant was subsequently able to suppress the viral load back to ≤ 400 HIV-1 RNA copies/mL and maintained virologic control for 24 weeks.

In our protocol, a combination of two bNAbs will be administered at the time ART is interrupted, and will likely have a persistent antiviral effect until levels wane to subtherapeutic levels, which we will assume to occur at about Week 12 of the ATI period. Also, we expect that in the post-ART and post-bNAb phase of the ATI that a period of acute viremia will occur, and that this could last for up several weeks. As described in Section 1.11, ART will be initiated if plasma HIV RNA levels remain consistently $> 50,000$ copies RNA/mL for four weeks, $> 10,000$ copies RNA/mL for six weeks, > 2000 copies RNA/mL for $>$

12 weeks, and > 400 copies RNA/mL > 24 weeks. In this scenario, post-treatment control will only be achieved once viremia falls below 400 copies RNA/mL and remains there for 24 weeks.

Success will hence be defined in two ways. First, subjects who fail to show any consistent rebound above 400 copies RNA/mL between Week 12 of the ATI (when bNAbs levels wane) and Week 36 of the ATI will be considered as having achieved post-treatment control. Second, subjects who exhibit a rebound and eventually achieve 24 weeks of virus control will be considered as having achieved post-treatment control.

Failure will be defined based on the need to resume ART due to high-level viremia, dropping CD4+ T cell counts, or clinical events (see Section 1.11).

The proportion of individuals who achieve our study-defined PTC will be the primary outcome.

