Primary efficacy outcome. All subjects will undergo a treatment interruption designed to evaluate the primary outcome of "post-treatment control" (PTC). The proportion of individuals who achieve PTC will be tabulated and a 2-sided 95% confidence interval obtained by exact calculations for the binomial distribution. For those who initiated ART during acute infection, a literature review indicates that no more than 15% PTC would be expected without intervention. For those who initiated during chronic infection, no more than 5% PTC would be expected. These maximum expected rates will serve as the null hypothesis for our P-value calculations. Evaluation of the acute group will be the primary analysis, while evaluation of the chronic group will be exploratory and provide initial preliminary information on generalizability.

Using standard and innovative measures of immunogenicity, we will determine the capacity of our vaccine strategies to stimulate broad, functional T cell responses against novel HIV epitopes, and comprehensively

characterize the impact of the vaccine on several innate and adaptive immune parameters. The size of the active and latent reservoirs before, during and after vaccination will be measured.

Power calculations. For the acute group, observing 6 or more PTC among N=15 (40%) will result in $P < 0.05$ versus the null hypothesis of 15%, and the study will have $\geq 80\%$ power if the true chance of PTC with intervention is $\geq 47\%$.

For the chronic group, observing even one PTC (20%) would provide some indication of promise, and observing 2 PTC (40%) would produce $P < 0.05$ versus the null hypothesis of 5%.

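### The controller exclusion misses people who controlled HIV during an earlier ART interruption; in a single-arm trial of post-treatment control they would probably count as successes without any treatment effect

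*Combined protocol and SAP*

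**What the plan says.** Section 6.3, item 8 (synopsis main exclusion 7) excludes elite "control prior to ART as defined by having HIV RNA levels below the limit of detection without exposure to ART, using commercially available assays" in use at the time. It is the only criterion that refers to viral control without drugs.

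Section 6.2, item 5 requires participants to be "On continuous antiretroviral therapy for at least 12 months without any interruptions of greater than 14 consecutive days within the last 1 year". Earlier interruptions are not restricted. The rule in section 6.3 item 4b and section 9.11 against interrupting therapy applies only when an old antibody-susceptibility result is reused.

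Section 15.4 takes its PTC definition from a cohort collaboration in which controllers stayed off ART for at least 24 weeks and "maintained viral loads ≤ 400 copies/mL for at least 2/3 of the time points". In this trial, success includes "subjects who fail to show any consistent rebound above 400 copies RNA/mL between Week 12 of the ATI" and Week 36. The synopsis instead defines the primary endpoint by a viral load below 50 copies/mL.

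Section 1.11 says that similar data were "reported by an extended collaboration that included several post-treatment controllers from our group". Section 6.1 states: "We will recruit HIV-infected adults who started ART in early infection from our local cohort (Options" being its name) and from other centres in the city.

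The synopsis and section 15.6 test PTC against fixed rates of 15% in the early-ART group (N=15, primary) and 5% in the late-ART group (N=5, exploratory). Both are described as the most that would be expected without intervention.

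**The concern.** Item 8 accepts the principle that people already known to control HIV without drugs should not be enrolled in a trial whose outcome is drug-free control. It applies that principle to one kind of controller only.

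- **Control during an earlier interruption.** A person who has taken ART falls outside item 8 by its wording. If the interruption ended more than a year ago, "without any interruptions of greater than 14 consecutive days within the last 1 year" does not exclude them either. The investigators' group has contributed known post-treatment controllers to a collaboration and recruits locally, so the case is plausible.
- **Low but detectable set-point before ART.** Item 8 cuts at the assay's limit of detection, while section 15.4 counts control at up to 400 copies/mL. A late-ART participant with an untreated set-point of, say, 200 copies/mL is eligible and could meet section 15.4 by returning to it. Under the synopsis endpoint (<50 copies/mL) the same person would not count.

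There is no control arm. If enrolment included more such people than the null rates allow for, a positive result could reflect who was enrolled rather than the regimen.

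**Working it through.** **Inputs.** Early group: N=15, null 15%, 6 or more PTC needed, power stated as at least 80% at a true rate of 47% (section 15.6). Late group: N=5, null 5%, 2 PTC needed (section 15.6). Test: likelihood ratio (synopsis). Assumed, because the documents give no figures: the number k of pre-existing controllers enrolled, their chance r of controlling again, and the no-effect PTC rate p in everyone else.

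**1. The plan's own figures.**
- P(X≥6 | 15, 0.15) = 0.0168; likelihood ratio P = 0.019.
- P(X≥5 | 15, 0.15) = 0.062; likelihood ratio P = 0.077. So 6 is the correct cut-off.
- Power at 47%: P(X≥6 | 15, 0.47) = 78.8%, just under the stated 80% (81.0% at 48%).
- Late group: P(X≥2 | 5, 0.05) = 0.023; likelihood ratio P = 0.018.

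**2. Early group with k certain controllers (r = 1).** The chance of 6 or more PTC without an effect is P(X ≥ 6−k | 15−k, p):

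| Rate p in the others | k=0 | k=1 | k=2 | k=3 |
|---|---|---|---|---|
| 15% | 1.7% | 4.7% | 11.8% | 26.4% |
| 10% | 0.2% | 0.9% | 3.4% | 11.1% |
| 5% | 0.01% | 0.04% | 0.3% | 2.0% |

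The implied no-effect rate for the whole group is (k + (15−k)p)/15. For k = 1, 2, 3 it is 20.7%, 26.3%, 32.0% with p = 15%; 16.0%, 22.0%, 28.0% with p = 10%; and 11.3%, 17.7%, 24.0% with p = 5%. The top row therefore describes a group enriched well above the null.

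**3. Early group when repeat control is uncertain.** The chance is the sum over j of P(J=j | k, r) × P(X ≥ 6−j | 15−k, p). With p = 15%:
- r = 70%: 3.6%, 7.3%, 13.6% for k = 1, 2, 3.
- r = 50%: 2.9%, 4.9%, 7.7%.

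**4. Late group.** One certain controller, others at 5%: P(at least 1 of 4) = 1 − 0.95⁴ = 18.5%, against 2.3% with none. At r = 70%: 0.7 × 18.5% + 0.3 × P(X≥2 | 4, 0.05) = 0.7 × 18.5% + 0.3 × 1.4% = 13.4%. Section 15.6 also says that "observing even one PTC (20%) would provide some indication of promise". With no controller the chance of at least one is 1 − 0.95⁵ = 22.6%; with one certain controller it is 100%.

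**The case against.** **The nulls already include spontaneous control.** This is the strongest point, and it stands. A rate of 15% in 15 people is 15 × 0.15 = 2.25 expected untreated controllers, and the plan calls the rate a maximum. If the overall no-effect rate stays at 15% and two of the 15 are certain controllers, the other 13 have a rate of (2.25 − 2)/13 = 1.9%, and the chance of 6 or more is about 0.01%, below the 1.7% baseline. Harm needs enrichment beyond the null. The documents do not show enrichment, and they do not say whether the literature behind the 15% excluded known controllers.

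**Earlier control does not guarantee repeat control.** A reader might infer that every such person is a certain success. Nothing in the documents supports a probability of 1, which is why step 3 varies it.

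**The 400-copy route depends on one of two definitions.** A reader might infer that anyone with a set-point up to 400 copies/mL will count as PTC. That follows only from section 15.4. It also bears mainly on the five late-ART participants, whose analysis is exploratory, since early participants began ART within six months of infection. The remark about a single PTC in that group is not a test.

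**No enrolled case is identified.** Section 1.11 does not say that the group's controllers belong to the recruitment cohort, have resumed ART or meet inclusion 5. This stands. It limits the size of the concern and leaves the gap in the criteria as it is.

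**The plan de-emphasises P-values.** Section 15 says interpretation will rest on estimates and confidence intervals. That does not remove the problem, because enrichment shifts the estimated proportion as well as the P-value.

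**Conclusion.** The gap in eligibility is real: no criterion excludes a person with documented control during an ART interruption that ended more than a year ago, and such a person would probably count as a PTC success without a treatment effect. This holds under either endpoint definition for anyone whose earlier control was deep enough. The second route, a low but detectable pre-ART set-point, holds under section 15.4 and not under the synopsis, and the two definitions must be reconciled.

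The size is uncertain. In the early group, one such participant leaves the false-positive chance below 5% in every scenario shown. Two or three take it above 5% under some assumptions (11.8% and 26.4% at the top of the range) but not others (0.3% and 2.0% with the others at 5%). The exploratory late group is more fragile: one certain controller moves the chance of 2 or more PTC from 2.3% to 18.5%. All of this rests on assumed numbers of controllers, assumed repeat control and assumed rates in the others. The documents do not support the stronger conclusion that a positive result would be spurious. They do leave that explanation unguarded in a single-arm design, and it is cheap to guard against.

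**What to change.** 1. Reconcile the PTC threshold between the synopsis (<50 copies/mL) and section 15.4 (400 copies/mL).
2. For any further enrolment, extend item 8 to people with documented off-ART HIV RNA at or below the reconciled threshold on two or more measurements, either before first ART (outside acute infection) or during any earlier interruption.
3. For participants already enrolled, identify such people from the complete ART history that section 9.1 already collects and from cohort viral loads. Pre-specify reporting of the PTC proportion, with its exact interval, with and without them, and tabulate pre-ART viral loads.
4. State whether the literature behind the 15% and 5% rates excluded known controllers.

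Appendix E shows participants already well into treatment at Version 2.2, and the documents do not say whether enrolment is still open, so item 3 may matter most. The cost is one sentence in the criteria, a chart review and one added analysis. The downside is the loss of a few candidates from a limited early-ART pool.

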7 CONCURRENT MEDICATIONS

All subjects should be maintained on the same medications throughout the entire study period, as medically feasible.

Subjects must provide their own antiretroviral drugs. No restrictions will be placed on the antiretroviral drug combinations. If medically feasible, study participants will be encouraged to remain on their entry antiretroviral regimen through week 34 of the study.

Participation in the study will not interfere in any manner with the subject's standard of care.

Given the potential immune-modifying activities of the vaccine and IL-12 adjuvants, other immunomodulatory drugs (e.g., cytokines, systemic corticosteroids, most biologics) will be discouraged if medically feasible.

Routine or standard of care vaccinations (such as influenza, pneumococcal, and meningococcal vaccinations) are allowed and documented in the case report forms.

8 STUDY TREATMENTS

[figure not shown]
8.1 Product management

[figure not shown]
[figure not shown]
[figure not shown]
[figure not shown]
The Investigational Drug Service (IDS) of the UCSF Medical Center Department of Pharmaceutical Services will be responsible for storage of all investigational products for this study. The IDS facilities include USP797-compliant IV preparation facilities, biohazardous preparation facilities and secure drug storage areas for drugs requiring monitored controlled room temperature, refrigeration (2-8 degrees C.), moderate freezing (-15 to -25 degrees C.) and deep cold storage (below -70 degrees C.). All facilities and departmental procedures are subject to inspection and oversight by the Board of Pharmacy, California State Department of Health, CMS and the Joint Commission.

The IDS has a long track record of supporting NIH-sponsored studies and has worked extensively with [name]'s HVTN unit. They have hence been through the rigorous DAIDS regulatory process and have in the recent past successfully supported local studies of VRC01 and other biologic products.

[figure not shown]
IAVI will manage the distribution of all investigation products. Working with the UCSF-based research pharmacy directed by [name], IAVI will collect and distribute all investigational products to the clinical site, and relabel any vials or cartons as needed. The cold-chain system will be reviewed and audited to ensure that all products remain viable. A 'critical document checklist' will be employed before shipping. Once all protocols and documents are established and checked, IAVI will and oversee shipment of each product. The group will proper cold chain for IP storage at the clinical site and generate a Cold Chain Assessment report.

